With respect to optimization of treatment, the key issues are the choice of sites for electrode positioning and the dosing strategy. In using the 1.25" diameter anterior electrode (as opposed to a smaller anode), the degree of focality is reduced and this should protect efficacy. We do not have sufficient knowledge of the functional neuroanatomy to justify greater focality (Nobler et al., 1994, Nobler et al., 2001, Seminowicz et al., 2004). Rather, at this stage, the more limited goals are to restrict seizure onset and expression largely to regions in the right prefrontal cortex (PFC), with virtually no stimulation in left PFC or left or right medial temporal lobe (MTL). In positioning the anode in the area of the Fp2 site in the 10/20 International EEG System, current density will peak broadly through the right anterior PFC. Furthermore, we have taken two steps to ensure that FEAST is not under-dosed. EEG seizures without convulsion are very rare with conventional ECT (Boylan et al., 2001), but may be more frequent with FEAST. Research groups differ in whether or not motor manifestations are required in defining the seizure threshold (ST). In this protocol, we will note the intensity level that results in an "EEG only" seizure, but require that EEG seizure manifestations be clear-cut and last at least 15 s to define the ST value used for subsequent dosing. Second, at any point after the fifth treatment, a clinical evaluation team can recommend a dosage increment, up to 9 x ST. Thus, in this first examination of FEAST, to protect efficacy we have deliberately erred on the side of sacrificing the degree of focality, while also allowing some flexibility in dosing. With stimulation at these levels, it is very unlikely that FEAST will be markedly ineffective, unlike low dosage RUL ECT ([name] et al., 1987b, [name] et al., 1993). Rather, to determine whether there is any effect on efficacy, a substantial number of patients will have to be treated in a masked, randomized protocol (which is planned following this study). Our published data (Nahas et al., 2013a) has demonstrated that FEAST has marked antidepressant effects. However, in the absence of a masked, randomized comparison with traditional ECT, equivalence in efficacy is unknown. This study focuses on the mechanistic issue and attempts to demonstrate that seizures induced by FEAST show robust electroencephalographic activity in frontal electrodes, but reduced activity in

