On 6 of 6 occasions at NYSPI with the anode at nasion, EEG seizures were evoked at the first or second step of titration (3-7 mC), most without motor expression and all markedly asymmetric in EEG expression. The seizures without motor convulsion were characterized by sharp spike activity, although unilateral slow wave activity was also present in some cases. These asymmetric EEG seizures had duration of between 8-35 s. On all 6 occasions titration continued and a motor convulsion occurred at a subsequent stimulus. These seizures were also markedly asymmetric in motor and EEG manifestations. Figure 2 presents a typical FEAST seizure with motor expression during the titration procedure. For comparison purposes a standard BL ECS (WIDE PW and 5 X ST) is also presented. The FEAST seizure occurred with stimulation at the minimum level for eliciting motor expression. The ECS seizure was with a dosage 2.5 times this ST, the convention used in a protocol comparing BL ECS to MST (Lisanby et al., 2003c, Moscrip et al., 2005, Dwork et al., 2004, Dwork et al., 2009). It is evident that on the side of stimulation (right) robust and classic spike-and-wave activity was manifested with FEAST. Each of the three NYSPI monkeys had one session in which the direction of stimulation was reversed (posterior to anterior). All 3 animals had motor seizures at the second step of titration (7 mC) that appeared to be more symmetric in motor and EEG expression. Finally, a fourth large male bonnet monkey (12 kg) was titrated with FEAST at the SUNY Downstate primate facility. The same procedures were followed except that the posterior electrode was made from a 20 gauge soft copper-grounding clamp (1.9 x 6.35 cm; 12.07 cm²). This smaller dimension allowed placement of the electrode anterior to the motor strip and the shorter length should further limit stimulation to temporal areas. The first two

Figure 2. EEG Seizure Expression with FEAST and ECS

stimulations resulted in asymmetric EEG seizure activity without motor expression; an asymmetric motor and EEG seizure was obtained at the third stimulation.

A potential theoretical concern might be that FEAST could concentrate current so intensely as to result in damage to neuronal tissue (Yuen et al., 1981, Agnew et al., 1983, Agnew and McCreery, 1987,

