eyebrow. The larger posterior electrode was concave in shape to better couple to the scalp. The posterior electrode was placed tangential to the midline and extended across the right supplementary motor cortex. The medial position of this electrode was adjacent to the line connecting the nasion and inion and with the posterior boundary 1.0 inch anterior to the vertex, with the lateral portion extending over the right hemisphere.

As the study began it became apparent that this 300 Ohm limit on dynamic impedance was too restrictive (there were frequent aborted stimuli due to the voltage limit being exceeded). To solve this practical issue in stimulus delivery, the anode electrode size was increased, first to 1 inch and then to 1.25 inches (MUSC). The posterior electrode size was also increased to 2 x 3 inches.

FEAST treatments were given in the morning, 3 times per week. The criterion for an adequate seizure was ≥ 20 s motor duration. Subconvulsive stimuli, which occurred only during titration sessions, were followed 20 s later by restimulation. At the first treatment, the empirical titration procedure was used to estimate seizure threshold (ST) ([name] et al., 1987c, [name] et al., 1987d, [name] et al., 1991). Dosing at subsequent treatments was substantially above seizure threshold (6xST) as it is now commonly adopted for UB RUL ECT ([name] et al., 2008, Loo et al., 2008). Given insufficient clinical progress, this dosage was increased in some instances to up to approximately 9xST prior to terminating use of FEAST.

The titration schedule we used combined 5 parameters, with a range of charge from 5.4 to 43.2 mC. (See Appendix II for the titration table and dosing schedule for the proposed study.) If a patient did not have an adequate seizure at the highest titration setting (43.2 mC) they exited the protocol and received conventional ECT. However all patients had adequate FEAST induced seizures by this titration step and none exited prior to receiving FEAST. Thus, the highest dosage that was used in this pilot study was 384.0 mC, 66.7% the maximal output of a standard US Spectrum 5000Q (576 mC).

[figure not shown]
Note how, with improvements in technique, the percent improvement and number of FEAST remitters has increased with time (left, first patient, right, recent). Early patients had lower currents and smaller electrodes.

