In an open label study, the investigators intend to test the feasibility, safety and efficacy of a new form of electroconvulsive therapy (ECT), referred to as focal electrically-administered seizure therapy (FEAST). A modified MECTA Spectrum 5000Q device will be used. This device will be capable of delivering unidirectional, ultrabrief stimulation with a montage involving a small circular electrode (anode, 1.25" diameter) and a larger rectangular electrode (cathode, 2" x 3"). The primary objective in using unidirectional stimulation with this electrode geometry is to increase the precision of anatomical targeting. FEAST should enhance the capacity to concentrate current density in regions implicated in therapeutic processes and minimize exposure of areas in which stimulation results in adverse cognitive effects. As an expression of this objective, FEAST is expected to result in therapeutic seizures with focal onset and limited generalization. This hypothesis will be tested by comparing the FEAST and UB RUL ECT samples in focality of seizure onset as assessed by EEG ictal measures. A four-lead EEG montage will be employed at every treatment with the expectation that FEAST treatments result in reduced seizure expression in left and right temporal leads compared to traditional UB RUL ECT. In addition, fMRI measures of resting connectivity will be collected before and immediately following the ECT course (24-96 hours post-treatment). It is

hypothesized that FEAST results in greater focality in connectivity alterations, with primarily a right frontal locus of effects.

A second hypothesis is that FEAST will represent a more efficient form of seizure induction. The FEAST patients in this protocol should have a lower seizure threshold (expressed in the minimal charge to elicit a seizure) compared to the contemporaneous matched reference group.

A third hypothesis is that FEAST should be of similar therapeutic potency with a superior side effect profile when compared to standard UB RUL ECT, the form of traditional ECT with the most benign adverse effect profile and robust efficacy (Loo et al., 2012).

The study is expected to be completed 3 years after the approval of this IDE.

B. Protocol

B.1 Patient Selection

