The criterion for an adequate seizure is ≥ 20 s EEG duration. Subconvulsive stimuli, which occur only during titration sessions, are followed 20 s later by restimulation. Up to 5 stimulations are permitted at titration. Using these criteria, across our two of our recent studies, only 3 out of 1,372 treatment sessions were terminated without an adequate seizure (all due to very high thresholds at the first treatment). Additional monitoring includes continuous display of three channels of ECG (leads I, II, IV), heart rate, blood pressure, and pulse oximetry. At each treatment, the 4 EEG channels are digitized and along with treatment parameters automatically entered into a database using the MECTA EMR (electronic Medical Record) software. The intervals to return of spontaneous respiration and eyes opening upon command are also recorded.

FEAST Stimulus Dosing. After completion of the pretreatment assessment battery, treatment with FEAST will begin. FEAST will be administered using a modified spECTrum 5000Q device. In this study, stimulation parameters at titration will be restricted to an ultrabrief electrical stimulus (0.3 ms pulse width) and unidirectional administration. The amplitude of the constant current during each pulse will also be fixed at 800 mA. Train duration (1.5-8 s) and pulse frequency (30-80 Hz) will be the primary parameters manipulated to adjust dosage relative to seizure threshold (see Table 4). [One suprathreshold setting involves increasing pulse width to 0.5 ms].

At the first treatment, the empirical titration procedure is used to estimate ST ([name] et al., 1987c, [name] et al., 1987d, [name] et al., 1991). This procedure at the first session ensures that the lowest charge needed to evoke a seizure is

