identified for each individual patient ([name] et al., 1994, American Psychiatric Association, 2001). Dosing at subsequent treatments will be substantially above seizure threshold. With traditional ECT and a RUL electrode placement, a dose of at least 6 times the initial seizure threshold (6xST) has been shown to be maximally effective (McCall et al., 2000, [name] et al., 2000b), with lower dosage resulting in reduced efficacy ([name] et al., 1987b, [name] et al., 1993). This is also the case when an ultrabrief stimulus is used with the RUL electrode placement ([name], 2004a, [name] et al., 2008, Loo et al., 2012). Thus, the minimum dosage for FEAST will be approximately 6xST in treatments administered after the first session [see Table 4]. Given insufficient clinical progress after at least 5 treatments, this dosage may be increased to up to approximately 9xST prior terminating use of FEAST. Since the seizure thresholds with an ultrabrief stimulus are very low ([name], 2004a, Loo et al., 2012), and are expected to be lower still with the use of FEAST, the absolute dosage administered will in almost all cases be well below that commonly administered with routine treatment in the community.

The criterion for determining ST will be EEG determined. In the past 28 patients at MUSC we are now sufficiently confident that FEAST seizures can be seen on EEG. We will also record motor movement cessation in the leg that has the BP cuff inflated.

Table 4. Titration and Dosing Schedule

Titration and Dosing Schedule					
Pulse Frequency (Hz)	Pulse Width (ms)	Train Duration (s)	Current (mA)	Total Charge (mC)	Dose Relative to Initial ST
20	0.3	1	800	9.6	
20	0.3	2	800	19.2	
20	0.3	4	800	38.4	
20	0.3	8	800	76.8	
40	0.3	8	800	153.6	
80	0.3	8	800	307.2	
Subsequent Dosing: 6 X ST					
20	0.3	6	800	57.6	6
30	0.3	8	800	115.2	6
60	0.3	8	800	230.4	6
90	0.4	8	800	460.8	6
90	0.5	8	800	576	3.75
Subsequent Dosing: 9 X ST					

30	0.3	6	800	86.4	9
60	0.3	6	800	172.8	9
90	0.3	8	800	345.6	9
90	0.5	8	800	576	7.5

The titration schedule to be used in the study and the prescribed dosing at treatments following the initial titration session are presented in Table 4. The titration schedule starts with a dose of 9.6 mc, which is nearly the lowest ever used in clinical or research use of ECT, reflecting the expectation that seizure thresholds will be very low.

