The primary aim of this study is to contrast FEAST and UB RUL ECT in these EEG measures of seizure onset and propagation. Specifically, we expect FEAST to show greater focality of seizure onset than UB RUL ECT, with seizure onset most manifest in the right frontal EEG with FEAST, and far greater activity in the left and right temporal leads with UB RUL ECT.

B.14 Quality Assurance and Data Management

A highly experienced rater will provide clinical ratings throughout the treatment period. Accuracy of the output of the FEAST device will be tested ([name] et al., 1994), and calibration signals regularly applied to the EEG recordings. The stimulus parameters used with the modified Spectrum 5000Q will both be recorded electronically and transferred to a database using the Spectrum's automatic EMR logging software. An experienced psychometrician will review all neurocognitive data. Data will be entered on digital forms using automatic flags for out-of-range and missing values. Any correction to a data record will be recorded in an audit notebook. The study database will be backed-up regularly.

B.15 Statistical Analyses

Data Screening. Data will be reviewed for extreme values. When distributional assumptions are not met, data will be transformed or nonparametric procedures used. Prior to statistical analyses, the study sites (MUSC vs. GRU) and treatment groups (FEAST vs. UB RUL ECT) will be compared in the baseline sociodemographic and clinical features, using ANOVA and log-linear analyses, with a liberal threshold to detect inequality ($P < 0.2$).

Hypothesis Testing. Even though this is a preliminary investigation, yielding effect sizes by which to power a subsequent randomized study, it is important to protect the Type I error rate by limiting primary analyses to a restricted and clearly specified set of hypotheses and outcome measures. The primary analyses will test the hypotheses stated below which address the objectives described in Section II. The major areas of investigation are effects on seizure threshold, electrophysiological (EEG) activity, efficacy, function, objective changes in cognition and subjective cognitive changes. The primary efficacy analyses will be conducted in the intent-to-treat sample.

Hypothesis 1. FEAST is substantially more efficient (i.e., lower ST) than traditional ECT, even when both use an ultrabrief (0.3 ms) pulse width.

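### Hypothesis 1 reads a lower EEG-defined seizure threshold as greater efficiency, although the same EEG rule may stop titration at a different event in the two arms

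*Combined protocol and SAP*

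**What the plan says.** Hypothesis 1 (Section IV.B.15) states: "FEAST is substantially more efficient (i.e., lower ST) than traditional ECT, even when both use an ultrabrief (0.3 ms) pulse width". The overview just before Section IV.B frames the same idea as a "lower seizure threshold (expressed in the minimal charge to elicit a seizure"). The analysis is one ANCOVA on log10 threshold with site and treatment group as factors and age and gender as covariates. No motor-threshold or sensitivity analysis is planned.

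The threshold rests on EEG. Section IV.B.6 says "The criterion for determining ST will be EEG determined" and "The criterion for an adequate seizure is ≥ 20 s EEG duration". Section III.D.2 gives a different duration; there the plan is to "require that EEG seizure manifestations be clear-cut and last at least 15 s to define the ST value used for subsequent dosing". That section also says the EEG-only intensity will be noted, and Section IV.B.6 says the end of movement in the cuffed leg will be recorded. Hypothesis 1 uses neither.

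On how often the EEG and the convulsion part company, Section III.D.2 says: "EEG seizures without convulsion are very rare with conventional ECT (Boylan et al., 2001), but may be more frequent with FEAST". The overview before Section IV.B expects FEAST seizures to start focally and generalise little.

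For UB RUL, Section IV.B.15 and Section IV.D.5 specify the same titration schedule, and Section IV.B.7 says the two groups are handled alike apart from listed differences. The RUL dosing paragraph of Section IV.B.6, however, says these patients follow the sites' usual clinical practice. It gives no threshold criterion.

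**The concern.** A threshold comparison measures efficiency only if titration ends at the same kind of event in both arms. On the protocol's own expectations it may not. In UB RUL the first adequate EEG seizure would nearly always be a convulsion. In FEAST it may in some patients be a non-convulsive seizure, reached one or more doubling steps before a convulsion would have occurred. A significant Hypothesis 1 result could then reflect a more efficient stimulus, an earlier stopping event, or both, and the planned model cannot tell these apart.

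The primate work points the same way. Most FEAST EEG seizures at the first or second step had no motor expression, and "On all 6 occasions titration continued and a motor convulsion occurred at a subsequent stimulus".

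Hypothesis 1 is among those tested in the primary analyses, and the study is meant to supply effect sizes for a later randomised trial, so a misread efficiency estimate would carry forward. If usual practice for UB RUL applies a motor criterion, the rule itself would differ by arm and the gap could be larger.

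**Working it through.** **Titration ladder.** The notes to Table 1 (Section III.D.6) give charge = 2 × current × pulse width × frequency × duration. With 0.8 A and 0.3 ms, the first step of Table 4 is 2 × 0.8 × 0.3 × 20 × 1 = 9.6 mC. The remaining steps reproduce as 19.2, 38.4, 76.8, 153.6 and 307.2 mC. Each step doubles charge, so one step is log10(2) = 0.301 on the Hypothesis 1 scale.

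**Size of the artefact.** If a share f of FEAST patients stops k steps below their convulsive threshold, the mean shift is f × k × 0.301. With k = 1:
- f = 10%: 0.030, ratio 0.93
- f = 30%: 0.090, ratio 0.81
- f = 50%: 0.151, ratio 0.71

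**Inputs the documents do not give.** There is no human EEG-only rate, step gap, SD or alpha. I assumed k = 1 and two-sided alpha 0.05. The 50-fold range in Section III.D.3 is log10(50) = 1.70 units; read as six or four SDs, this gives an SD of 0.28 or 0.42. I used 0.25 to 0.35. The 40 per arm is the completer target in Section IV.B.1.

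**Simulation.** I ran 10,000 trials per setting. Log-normal convulsive thresholds were identical in both arms and mapped to the six-step ladder. A share f of FEAST patients was moved down one step, but not below 9.6 mC. A t-test on log10 threshold stood in for the ANCOVA.

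| EEG-only share in FEAST | Median 10–15 mC: apparent reduction | False FEAST-lower result | Median 30–60 mC: apparent reduction | False FEAST-lower result |
|---|---|---|---|---|
| 0% | 0% | 2–3% | 0% | 2–3% |
| 5% | 2–3% | 3–4% | 3–4% | 4% |
| 10% | 4–5% | 4–6% | 6–7% | 6–7% |
| 30% | 10–15% | 12–24% | 17–19% | 18–29% |
| 50% | 17–24% | 28–55% | 28–29% | 41–65% |

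**Which medians are plausible.** Section III.D.6 says every patient in the first pilot series had an adequate seizure by 43.2 mC, under a motor criterion. Medians of 30 to 60 mC put 26% to 72% of patients above 43.2 mC; the chance that none of 17 would be above it is then under 1%. Medians of 10 to 15 mC put 0.6% to 9.5% above it and fit better. Early pilot patients were also titrated on current, so this is a plausibility check, not proof.

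**Primate evidence.** Section III.D.4 gives 8 to 35 s for the EEG-only seizures. The shorter ones would not satisfy either the 15 s or the 20 s rule, so they would not end titration here. Those titrations also used a motor seizure as the endpoint for re-stimulation. The evidence is indicative only.

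**The case against.** The strongest reply is that the definition is deliberate and disclosed. Section III.D.2 acknowledges that groups differ on requiring motor signs. The hypothesis concerns the least charge that produces a seizure, the schedule is common to both arms, and Hypothesis 2 separately tests whether FEAST seizures are weaker and more focal. On that definition a lower EEG threshold is a real finding, and FEAST is designed to limit generalisation. This stands, and it is why the planned analysis should remain. It does not support the further step from a lower EEG threshold to efficiency for a comparable seizure.

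Four stronger readings are tempting but unsupported:
- A reader might infer that FEAST is not more efficient, or that a positive result would be false. The documents show neither; pilot thresholds under a motor criterion were also low.
- A reader might take a large bias as likely. No human EEG-only rate is given, and at shares of 10% or less the effect is small.
- A reader might infer that all cited FEAST results used a motor threshold. The statement "The criterion for an adequate seizure was ≥ 20 s motor duration" is shown only for the first 17 patients. The criterion for the later 18 cannot be seen in the text available for this review.
- A reader might therefore infer that the threshold multiples used for dosing differ in meaning from the whole pilot experience. That rests partly on the same unseen criterion.

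**Conclusion.** The concern holds as a limit on interpretation. The planned model cannot separate stimulus efficiency from a different stopping event, the protocol itself gives reason to expect the difference, and whether UB RUL uses the EEG criterion is unresolved. The size is unknown. Under equal convulsive thresholds, 40 per arm and a one-step gap, the false-positive rate runs from near the nominal 2.5% in FEAST's favour, when few endpoints are EEG-only, to more than half of trials at a 50% share under some of the assumed distributions. The share, gap, SD, medians and alpha are all assumptions. A change to the plan is worthwhile because the data needed are already recorded and the wording of the conclusion depends on them.

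**What to change.** 1. Keep the EEG-threshold ANCOVA as the Hypothesis 1 analysis.
2. State that one EEG criterion defines the analysed threshold in both arms. Reconcile the 15 s rule in Section III.D.2 with the 20 s rule in Section IV.B.6, and the usual-practice wording for RUL in Section IV.B.6 with Section IV.B.7.
3. From the EEG and cuffed-leg data already recorded, report by arm the share of threshold seizures without motor expression.
4. Add a supportive sensitivity analysis of the convulsive threshold with the same covariates. Treat an EEG-only endpoint as right-censored at the recorded step, or as interval-censored up to the first later charge that gave a motor seizure.
5. If the EEG-only share differs by arm, or the sensitivity analysis does not support the result, word the conclusion as a lower EEG-seizure threshold and not as greater efficiency for a comparable seizure. Do not require both tests to be significant.

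The cost is SAP wording, one descriptive table and one extra model. That model will be imprecise. Later treatments start near six times threshold, so an interval spans about log10(6) = 0.778, or 0.778 / 0.301 = 2.6 doubling steps. It also assumes a threshold that is stable across sessions, while Section III.C.5 describes anticonvulsant effects over the course. This is why it should support the main analysis and not act as a gate. No dosing change is implied.
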